4.2. Criteria for Recruitment and Recruitment Process

The participants will have undergone visual acuity testing, clinical examination and optical coherence tomography screening and deemed to have nAMD or DME that requires treatment with IVT, and with no other significant vision-threatening disorders (see section on inclusion/exclusion criteria), by their treating physician as part of clinical care. The study population will be recruiting from retinal outpatient clinics in a single tertiary centre (SNEC) where retinal clinics are conducted and eligible patients will be identified by the consulting physician and referred to the clinical research coordinator (CRC) during their clinic appointment. The CRC will approach the patient and provide details of the study and further confirm the eligibility for the study before informed consent is obtained.

4.3. Inclusion Criteria

Inclusion criteria will include patients with chronic macula disease including those diagnosed with nAMD and DME, who require IVT. This would include treatment naïve patients (no IVT in either eye the last 6 months) and previously treated patients who have had IVT in either eye in the last 6 months and require further IVT treatment at the baseline study visit in either eye. All participants will be able to provide

informed consent, speak English or Mandarin, be a Singapore resident and must consent to undergoing the MPI intervention.

4.4. Exclusion Criteria

Exclusion criteria include patients who are unwilling or unable to perform CAT testing, those that are unable to provide informed consent, and those with other significant eye pathology such as cornea problems, glaucoma, or other retinal diseases that may substantially affect vision. Exclusion criteria assessed by the clinical research coordinator will include those that do not speak English or Mandarin fluently, cognitive impairment (as assessed using 6CIT of ≥ 8), or obvious observable physical or hearing disabilities that prevents them from completing the CAT questionnaire and undergoing MPI effectively.

5. STUDY DESIGN AND PROCEDURES/METHODOLOGY

This study comprises two study designs running in parallel: (Cohort 1) Comprises of a prospective randomized control trial (RCT) study with two arms to assess the overall effectiveness of MPI, a personalized intervention based on the use of specific sub-optimal CAT QoL domain scores, versus standard care, to improve adherence rates to IVT, and improvements in QoL, VA, and CS, and to increase disease free intervals assessed on OCT, in patients with nAMD or DME receiving IVT and having suboptimal CAT scores. atSNEC; (Cohort 2) For those patients who do not have suboptimal CAT scores, they will continue to be enrolled in a prospective observational cohort study, and undergo routine clinical care.

- Participants who meet the eligibility criteria and provide informed consent will be enrolled and assigned a unique study identification number, before proceeding with study procedures.
- CAT scores will be collected via a hybrid remote or in-clinic delivery method. At baseline, CATs will be administered in-clinic or via CAT links sent by WhatsApp to their contact number. At subsequent timepoints, relevant CAT links will be sent via a WhatsApp message to their designated contact number, to complete the questionnaire remotely on their own SMART device, before their appointment (**Figure 1**). Those who are unable to complete CAT testing remotely will be given an additional opportunity to complete them in-clinic using an internet enabled tablet in person at their clinic visit with/without CRC assistance (**Figure 1**). The CAT scores will be assessed by clinical research coordinator.
- Following baseline assessment, **participants with suboptimal CAT scores (Cohort 1-<50 in any domain)** will be included in the RCT and randomly allocated in a 1:1 ratio to either the intervention group (personalised multi-disciplinary protocolised intervention, MPI) or the control group (standard care). Randomisation will be conducted using a computer-generated random sequence created by an independent biostatistician not involved in recruitment or outcome assessment. To ensure balance across disease types, randomisation will be stratified by diagnosis (neovascular age-related macular degeneration [nAMD] vs. diabetic macular edema [DME]). Allocation concealment will be maintained using sequentially numbered, opaque, sealed envelopes prepared by an independent study coordinator. The envelopes will only be opened after baseline data collection to assign participants to their respective groups. Co-Is that are not treating clinicians and data analysts will remain blinded to group allocation, although masking of participants and principal investigator and Co-Is who are the treating clinicians will not be feasible due to the nature of the intervention.

- For the MPI arm, the CAT scores integrated into the electronic medical records will be used to formulate **an automated protocolized standardized MPI for all patients based on the domain specific scores that are sub-optimal** (See **Table 2**). All MPI patients will receive *a medical consultation (compulsory) and an addition of Intervention 1-4 (electives, 1) NE, 2) OP, 3) OT, 4) SW*. In the MPI arm, these referrals would be automatically triggered by the study team based on baseline CAT scores and the treating clinician will be informed. The MPI visits will take place on the same day as standard clinical visits where possible, however additional MPI study visits may be needed if there are scheduling challenges. Referral adherence to the MPI appointments and intervention will be assessed.

Sub-optimal scores are defined as any domain where the scores are below 50 at baseline or have reduced by 25% from the baseline visit. Table 2 summarizes the MPI interventions that are relevant to each CAT domain. A tailored MPI will be formulated and recommended to the patient at baseline, or at a follow-up time-points where domain scores decrease, and the MPI should be completed within 4 months.

Table 2: Standardised personalised MPI based on sub-optimal CAT domain-specific scores

| Ret CAT | | MacCAT | |
|---------------------|---------------|---------------------|---------------|
| Item Bank | Interventions | Item Bank | Interventions |
| Visual symptoms | (2) | Activity Limitation | (2), (3) |
| Activity Limitation | (2), (3) | Lighting | (2) |
| Emotional | (1), (4) | Emotional | (1), (4) |
| Health Concerns | (1), (4) | Concerns | (1), (4) |
| Convenience | (1), (4) | AMD management | (1), (4) |
| Lighting | (2), | | |
| Social | (4) | | |
| Economic | (4) | | |

- In the standard care arm, the treating clinician will be masked from the CAT scores and will use his/her own discretion when recommending the treatment regimen or when making any appropriate nurse or allied health referrals, independent of the CAT scores. The CAT scores will be recorded by the clinical research coordinator at baseline and follow-up visits for comparison to the MPI arm.
- For those patients who do not have sub-optimal CAT scores at baseline, they will be assigned to an observational study group (Cohort 2) to continue to undergo routine clinical care and at the assigned study time points, they will be reassessed for any changes in their CAT scores and will undergo randomisation into the RCT if their scores have dropped below 50 or have reduced by 25% from the baseline visit. For those patients who do not experience sub-optimal CAT scores or a significant drop in their CAT scores during the duration of the study, they will still have their data collected at

all study visits based on the protocol but will not undergo randomisation. If any of these cohort patients show non-adherence to clinic visits during the duration of the study, they will be eligible for “rescue” MPI according to the clinician’s discretion at their next study visit and will be analysed as a separate sub-group.

Study schedule and outcome measures

The primary outcome is the comparison of adherence rates to IVT treatment between the MPI arm versus standard care (Cohort 1) at 6, 12 and 18 month time points (+/- 8 weeks) (main outcome) (Specific aim 1). The follow-up study visits will be coordinated with the planned clinical standard care visits, only if the patient does not have a routine clinical care visit scheduled within the range of the follow-up time-points will an additional study visit be scheduled.

Adherence is defined as

- 1) patient attends all follow-up appointments within 1 month of the planned follow up date, and
- 2) patient receives IVT within 1 month of when the doctor recommends IVT.

At each follow up time point, based on the previous scheduled follow-up appointments and recommended IVT schedule, the study team will assess if the patient has been “adherent” or “non-adherent”. If the patient does not visit the clinic within the range of the follow-up time points or does not attend the scheduled study visit, phone calls will be made to determine reasons or barriers for adherence. A remote invitation to complete the CAT questionnaire will also be sent to these patients or if uncontactable, they will be approached and interviewed at their next clinical visit. For previously treated patients, previous adherence status up to 2 years prior to study enrolment for the time of IVT treatment will be recorded by the study team from medical records.

Secondary outcome measures will be assessed at baseline and 6, 12, and 18 month follow up visits (+/- 8 weeks) including:

- CAT scores (Specific aim 2A) from the CAT questionnaire database
- Visual function -Monocular and binocular presenting corrected VA and CS (Specific aim 2B) will be collected from the clinical records. If data are not present, the CRCs will conduct these tests on participants using standardized protocols.
- Disease free intervals as defined by the maximum IVT treatment interval where no disease activity recurrence is detected on OCT will be collected from clinical records and OCT images from the clinical database (Specific aim 2B)
- Tertiary outcome measures include the acceptability, adoptability, appropriateness, feasibility, fidelity through mixed method testing with interviews and questionnaires (Specific aim 3).
- The costs of MPI, baseline and 18-month assessment of Euro-quality of life (EQ-5D) to assess QALYs (Specific aim 4)

Qualitative and quantitative analysis of key stakeholders (Specific aim 3)

The PI, assisted by their Co-Is and collaborators, will identify eligible individuals for qualitative interviewing that will be performed with major stakeholders between 6 to 15 months timeline. These include the clinicians, nurses and the allied health specialists (OP, OT and SW) who will be involved in administering the MPI, and patients and care-givers who receive the MPI. Potential individuals will be contacted over email or phone call, and a trained study team will follow up on affirmative responses by obtaining written informed consent to carry out the following study procedures:

Qualitative protocol: Semi-structured (1-on-1) interviews with the above key stakeholders will be conducted to explore their perspectives on barriers and enablers of integrating MPI into a Singapore public hospital for the management of nAMD and DME patients receiving IVT. Purposive and snowball sampling will be used to ensure all stakeholder groups are represented. Interviews will be conducted until no new data emerges.

An interview guide will be developed, underpinned by a suitable implementation research framework such as the NASSS framework (the non-adoption, abandonment, scale-up, spread, and sustainability framework)⁶⁰ which was created for planning and investigating implementation of health interventions. We will include interview questions that help elicit stakeholder perspectives on implementation outcomes salient to future implementation success, e.g. adoption, acceptability, appropriateness, feasibility, and fidelity, as defined by Proctor et al 2011⁶¹.

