7. DATA ANALYSIS

7.1. Data Quality Assurance

Participants information(data) from medical records dating up to 10 years prior and up to 24 months after informed consent is obtained will be collected. Linkage of participant identifiers to sociodemographic and questionnaire data can only be done on the request of the PI. The Investigator(s)/ Singapore National Eye Centre will permit study-related monitoring audits, MCRC and or EC review and regulatory inspection(s), providing direct access to source data/ document.

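### The primary adherence endpoint carries a +/-8-week visit window, with no fixed end date for the adherence period and no rule for items whose 1-month grace is still open

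*Protocol*

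**What the plan says.** Protocol section 5 (study schedule and outcome measures) defines the primary outcome as adherence in the MPI arm against "standard care (Cohort 1) at 6, 12 and 18 month time points (+/- 8 weeks) (main outcome"; section 8.1 names 18 months as the main time point. A patient is adherent only if two conditions both hold. On appointments: "patient attends all follow-up appointments within 1 month of the planned follow up date, and". On injections: "patient receives IVT within 1 month of when the doctor recommends IVT".

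On timing of the classification: "At each follow up time point, based on the previous scheduled follow-up appointments and recommended IVT schedule, the study team will assess" whether the patient is adherent. No cut-off day is given. Visit dates follow the clinic diary: "The follow-up study visits will be coordinated with the planned clinical standard care visits, only if the patient does not have a routine clinical care" (the sentence goes on to provide an additional study visit in that case). For a patient with no visit in range, the protocol provides phone calls about reasons and a remote CAT invitation, but no date or rule for the adherence classification.

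The same window is then applied to the secondary measures (CAT scores, VA, CS, OCT-based intervals). Section 8.2 tests the percentage adherent with a chi-square or Fisher's exact test. Section 7.1 covers medical records "dating up to 10 years prior and up to 24 months after informed consent is obtained will be collected".

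**The concern.** A window of +/-8 weeks suits a measurement taken on one day, such as visual acuity. Adherence here is different: it summarises everything since follow-up began, and any one lapse makes the patient non-adherent. A patient assessed late has had more appointments and injections at which to lapse than one assessed early. A test of two proportions treats both as if observed for the same time.

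The end of the period is also loose. An injection recommended, or an appointment planned and missed, in the month before assessment is neither a success nor a failure yet, and the protocol does not say how it counts.

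What is at stake is comparability of the primary endpoint between patients and possibly between arms. Arms could differ because the visit date follows the treatment schedule. The MPI consultation includes discussing longer intervals between injections (section 1), and Hypothesis 2B expects longer disease-free intervals under MPI. Treating clinicians are not masked (section 5).

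**Working it through.** **Inputs.** From the protocol: time points 6, 12 and 18 months, window +/-8 weeks (section 5); non-adherence 40% under standard care and 20% under MPI, 80% power, two-sided 5%, 79 per arm, 160 rounded, 200 after 20% dropout (section 8.1). Assumed here: a constant rate of first lapse, set to give 40% and 20% at 18 months.

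**The plan's own figure.** With unpooled variance, n = (1.96 + 0.84)² × (0.4×0.6 + 0.2×0.8) / 0.2² = 78.5, so 79 per arm; 160 / 0.8 = 200. Both reproduce. The pooled formula needs 82 per arm, so it gives 79% power at 80 per arm. That is the reference for the power figures below.

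**Length of observation.** One month is 30.44 days, so 8 weeks = 56 / 30.44 = 1.84 months.

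| Time point | Earliest | Latest | Longest/shortest |
|---|---|---|---|
| 6 months (26.1 weeks) | 18.1 weeks | 34.1 weeks | 1.88 |
| 12 months (52.2 weeks) | 44.2 weeks | 60.2 weeks | 1.36 |
| 18 months (78.3 weeks) | 70.3 weeks (16.2 months) | 86.3 weeks (19.8 months) | 1.23 |

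**Effect on the endpoint at 18 months.** Non-adherence at t months = 1 − (1 − p)^(t/18).

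- p = 40%: 36.8% at 16.16 months and 43.1% at 19.84 months, a spread of 6.3 points.
- p = 20%: 18.2% and 21.8%.

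**Effect on the comparison (80 per arm).**

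- Both arms early: 36.8 − 18.2 = 18.6 points, power 76%.
- Both arms late: 43.1 − 21.8 = 21.3 points, power 83%.
- Arms shifted 4 weeks each in opposite directions: 17.5 points (power 68%) or 22.5 points (power 88%).
- Arms shifted the full 8 weeks each in opposite directions, an extreme case: 15.0 points (power 55%) or 24.9 points (power 94%).
- No true effect, one arm assessed 4 weeks (0.92 month) later on average: 1 − 0.6^(18.92/18) = 41.5%, so 41.5 − 40.0 = 1.5 points of spurious difference.

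**How much can attendance alone do?** Attending more than 1 month after the planned date is already non-adherence. Late attendance can therefore lengthen the observation of a still-adherent patient by about 1 month at most: 1 − 0.6^(19/18) = 41.7%, or 1.7 points if every patient in one arm came a full month late and none in the other did. The rest of the 36.8% to 43.1% spread comes from planned visit dates.

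**Are the records there for a fixed cut-off?** Eighteen months plus 1 month of grace is month 19, inside the 24-month limit for a patient randomised at or near consent. For a Cohort 2 patient randomised at month 6, it is 6 + 18 + 1 = month 25 after consent; at month 12, month 31. Both are outside it.

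**The case against.** The strongest reply is that this is a data-handling detail for a statistical analysis plan, which is not shown. That would be fair if the protocol were merely silent. It is not: it attaches the window to the primary outcome and has the study team classify patients during follow-up. A later plan could repair this, but the protocol's own rule is a poor one for this kind of endpoint. The Cox model in section 8.2 is the adjusted analysis and does not alter the primary comparison.

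Two stronger readings are tempting and should not be made. First, a reader might infer that the last appointment or injection is judged before its grace has run. The protocol does not say that; it leaves open items without a rule, and an appointment attended as the study visit is already resolved. Second, a reader might infer that a patient who misses the window is classified only after 19.8 months, so that the observation period is driven by the patient's own attendance. The text opens "If the patient does not visit the clinic within the range of the follow-up time points or does not attend the scheduled study visit, phone" and goes on to provide for calls about reasons. Classification is not postponed, and it is drawn from scheduled appointments, not from an attended visit. The visit date follows the planned clinic schedule first, and the bound of about 1 month above limits what attendance can add.

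It is also right that the size rests on assumptions. Section 8.1 calls 40% a baseline rate, not a cumulative 18-month risk. Section 5 does not say whether later assessments cover the whole period or only the time since the previous one. No figure shows visit timing differing by arm, and if both arms shift together the effect is small. These points limit the size of the concern; they do not supply the missing cut-off.

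**Conclusion.** The point holds as a weakness in the definition of the primary endpoint: a visit window is placed on an any-lapse status, and the protocol states neither an end date for the adherence period nor a scoring rule for items with open grace. Periods of unequal length are certain to be possible (ratio 1.23 at 18 months, 1.88 at 6 months). Bias between arms is only possible. Under a constant lapse rate it is about 1.5 points for a 4-week difference in mean timing, and 6.3 points in the extreme case of the two arms at opposite window edges with no true effect. Different treatment intervals under MPI and unmasked clinicians make differential timing plausible, but the protocol gives no evidence that it will occur. The sample size of 79 per arm is not called into question by this point. The change is worth making because it is cheap and removes avoidable discretion from the primary endpoint.

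**What to change.** In section 5, separate the adherence cut-off from the visit window:

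- Score adherence from clinic records for every randomised patient at fixed calendar cut-offs of 6, 12 and 18 months after randomisation, whatever the visit date and whether or not a study visit took place.
- Count every appointment and IVT recommendation due on or before the cut-off, and let each run its full 1-month grace before it is scored.
- Keep +/-8 weeks only for CAT, VA, CS and OCT.

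Cost: mainly protocol wording, and status is read about 1 month after each cut-off. The planned rates and the sample size stay as they are. It is not wording alone for Cohort 2: for patients randomised at month 6 or later, the section 7.1 limit of 24 months after consent must be extended to cover 18 months plus the grace period from randomisation, with whatever consent and ethics approval that longer record collection requires.

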The proposed MPI consists of a medical consultation to optimise patients' treatment regimen, address concerns about their disease and treatment, explain advantages and disadvantages about the type of IVT medication and potential of increased treatment intervals between IVT, and address other patient and care-giver concerns.

Importantly, CAT scores will be available to the clinician to guide the consultation. Based on sub-optimal CAT scores, referral to one or a combination of services will be initiated by the study team according to a preset protocol (**Table 2**):

- (1) a referral to NE, which would include a session with a trained IVT nurse educator, who would use previously validated hard copy and digital education resources to educate the patients on their disease, symptoms, progression, and need for treatment. Factors which may cause anxiety for IVT patients such as side effects and adverse events will be addressed and the need for IVT adherence to maintain long-term vision will be reinforced. The patients would be reminded about the availability of the IVT hotline to address concerns and appointment issues.

- (2) a referral to OP who, after a needs assessment, would then carry out a comprehensive low vision assessment that includes refraction, CS, reading acuity, determination of reading goals and prescribing of suitable optical aids. OPs will assess and address any vision-related issues that may hinder reading specific tasks, navigation and other ADLs, which may be barriers to IVT adherence. They can further discuss the patient's expectations about their visual recovery and the need for IVT to maintain vision.
- (3) a referral to OT who, after a needs assessment, would provide advice about optimal lighting and, contrast perform activities of daily living retraining and functional/community mobility training, provide patient/family education and, if required, home modification to facilitate independence in ADLs, which may may allow better access to IVT appointments promoting adherence.
- (4) a referral to medical SW who, after a needs assessment, would provide the necessary emotional counselling, financial counselling and referral to community care services and other relevant support services addressing relevant barriers related to adherence to IVT.

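### The protocol gives the primary adherence classification to the study team without reserving it for the staff it keeps blinded

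*Protocol*

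**What the plan says.** Protocol section 5, under the study schedule and outcome measures, makes adherence the primary outcome, compared between MPI and standard care at 6, 12 and 18 months. It has two components, both required: "patient attends all follow-up appointments within 1 month of the planned follow up date", and "patient receives IVT within 1 month of when the doctor recommends IVT". On who decides, the same section says that at each time point "the study team will assess if the patient has been" adherent or non-adherent, working from the earlier appointments and the recommended injection schedule.

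The study team also has a role in delivering the intervention. In section 5, for the MPI arm, "these referrals would be automatically triggered by the study team based on baseline CAT scores". Section 1, where the MPI is described, says likewise that "referral to one or a combination of services will be initiated by the study team according to a preset protocol".

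On masking, section 5 states that "Co-Is that are not treating clinicians and data analysts will remain blinded to group allocation", whereas "masking of participants and principal investigator and Co-Is who are the treating clinicians will not be feasible". The only person expressly kept apart from outcome assessment is the one who prepares the random sequence, "created by an independent biostatistician not involved in recruitment or outcome assessment".

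**The concern.** Participants and treating clinicians cannot be masked, so masked assessment of the primary outcome is the main protection against biased ascertainment still available. The protocol has blinded staff but does not assign them this task. It assigns it to a group described with the same words as the group that starts arm-specific referrals.

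This matters because classification is not fully mechanical. Someone has to settle three questions that section 5 leaves open:

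- which date is the planned one after a visit has been moved;
- which recommendation starts the 1-month clock if the injection plan changes;
- whether additional MPI visits, which section 5 allows, count among the follow-up appointments that must all be attended.

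The first two can be related to arm, because the MPI consultation is meant to optimise the regimen and discuss longer injection intervals (section 1). The third arises only in the MPI arm. Patients who miss a visit are also telephoned for reasons (section 5), so an assessor may know both the arm and an explanation when judging a late visit. Since all appointments must be on time, one borderline item can change a patient's status.

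**Working it through.** **Step 1. Who does what, and who knows the arm (Protocol sections 1 and 5).**

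| Task or state | Assigned to |
|---|---|
| Start MPI-arm referrals | Study team |
| Classify adherence | Study team |
| Kept blinded | Non-treating co-investigators, data analysts |
| Cannot be masked | Participants, principal investigator, treating co-investigators |
| Stated to be outside outcome assessment | Biostatistician who creates the sequence |

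No row or sentence joins classification to the blinded group. Assessment with knowledge of the arm is therefore permitted, though not prescribed.

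**Step 2. The plan's own figure (section 8.1).** Inputs: 40% versus 20% non-adherence, two-sided 5%, 80% power; the 1:1 ratio is in section 5. With the unpooled normal formula,

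n = (1.960 + 0.842)² × (0.4 × 0.6 + 0.2 × 0.8) / 0.2² = 78.49, so 79 per arm, which agrees.

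The total is rounded to 160, and 160 / (1 − 0.20) = 200, which also agrees. The sample size is not affected by this point. It supplies the setting for step 3: 200 × 0.80 / 2 = 80 evaluable patients per arm.

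**Step 3. Sensitivity to differential misclassification (illustration).** Assume no true effect, with 40% truly non-adherent in each arm, and that a number of MPI patients equal to m percentage points of the arm are wrongly called adherent, with no errors in the other direction. Recorded non-adherence is then 0.40 in the control arm and 0.40 − m in the MPI arm. The rejection probability is the sum, over all pairs of counts (x, y) from 0 to 80, of

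Bin(x; 80, 0.40) × Bin(y; 80, 0.40 − m)

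for the pairs where the 2×2 chi-square statistic exceeds 3.84.

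About 0.40 × 80 = 32 MPI patients are truly non-adherent, so m can also be read as a share of those 32.

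| Shift m | MPI patients reclassified (80 × m) | Share of the 32 | Uncorrected chi-square | Continuity-corrected |
|---|---|---|---|---|
| 0 | 0 | 0% | 4.7% | 3.2% |
| 4 points | 3.2 | 10% | 7.9% | 5.8% |
| 5 points | 4.0 | 12.5% | 9.8% | 7.3% |
| 8 points | 6.4 | 20% | 18.3% | 14.4% |

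Both versions are shown because section 8.2 names the chi-square or Fisher's exact test without saying whether a correction applies. Whole patients give slightly lower values for the uncorrected test: 3 of 80 (3.75 points) gives 7.5%, and 6 of 80 (7.5 points) gives 16.6%.

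**The case against.** **The study team is not shown to be unmasked.** A reader might infer that an unmasked team classifies the outcome and that the same individuals do both tasks. The documents do not say so. The protocol uses study team loosely, for referrals, adherence, record review, interviews and safety review, and the blinded co-investigators may belong to it. This objection stands. What is left is that the protocol does not say which members classify.

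**The blinded staff do have a part in the primary endpoint.** A reader might conclude that they have none. That goes too far: blinded data analysts would be expected to run the primary comparison. What is missing is their assignment to the classification that comes before it.

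**The endpoint is largely objective.** Two date windows are applied to dates set beforehand, with no grading or image reading, and detailed rules for rescheduled visits may sit in a statistical analysis plan that is not shown. This carries weight and makes the risk smaller than for a subjective outcome. It does not dispose of the point, because the protocol itself names the assessor, and who classifies is a separate question from how the dates are derived.

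**The shifts are assumed and all in one direction.** Correct. Reclassifying a fifth of the truly non-adherent MPI patients would be severe for a date rule, and with continuity correction the 4-point case only just exceeds 5%. The table shows how sensitive the test is, and predicts nothing.

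**Masked classification is a partial remedy.** Also correct. Unmasked clinicians set the planned dates and recommend injections, and a masked assessor inherits any arm-related difference in those inputs.

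**Conclusion.** The point holds as a gap in the protocol. The primary classification is given to the study team, a term shared with those who start MPI-arm referrals, and nothing reserves it for the blinded non-treating co-investigators or data analysts. Assessment by staff who know the arm is therefore permitted, and some judgement remains despite the date-based definition.

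A reader might go further and conclude that biased assessment is built into the design, or that the trial's false-positive rate will be 18%. Neither follows. The documents give no misclassification rate, and the rates of 7.9% to 18.3% (5.8% to 14.4% corrected) rest on assumed errors that all favour MPI, with 40% non-adherence in both arms and 80 patients per arm. The sample size of 79 per arm and 200 in total is unaffected. The change should be made because it is cheap and uses staff already in the plan.

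**What to change.** In section 5, replace the sentence that gives the classification to the study team with one stating that:

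- the blinded non-treating co-investigators or data analysts classify each patient;
- they work from an extract of appointment, injection-recommendation and injection dates, with arm, MPI referrals and MPI visits removed;
- the existing 1-month windows are applied by one rule for rescheduled visits and changed recommendations, identical in both arms and written down before the first 6-month classification.

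Removing MPI visits means that they do not count among the follow-up appointments, and the protocol should say so. The change need not, and should not, introduce a new reference date such as the one set at the last attended visit: that would redefine the primary endpoint, and the documents give no support for it.

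The cost is a protocol wording change and some data preparation. MPI entries have to be stripped with care, because MPI visits may fall on the same day as clinic visits and the MPI-arm CAT scores sit in the electronic record, so open access to the record could reveal the arm. No new staff, visits or patients are needed. The influence of unmasked clinicians on planned dates and injection recommendations remains and should be acknowledged as a limitation.
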